10.3.2.4 Assessment of Liver Elevations

According to FDA's Guidance for Industry Drug-Induced Liver Injury: Premarketing clinical evaluation (July 2009), when aminotransferase (AT) abnormalities indicating hepatocellular injury are accompanied by evidence of impaired hepatic function (bilirubin elevation $> 2 \times$ ULN), in the absence of evidence of biliary obstruction (i.e., significant elevation of ALP) or some other explanation of the injury (e.g., viral hepatitis, alcohol hepatitis), the combined finding (i.e., Hy's Law cases) represents a signal of a potential for the drug to cause severe DILI.

For the purpose of assessing for potential Hy's law cases, the frequencies and percentages of subjects with post baseline liver specific function test values that meet the following criteria of potential clinical interest will be summarized by "as treated" treatment group:

- ALT $\geq 3 \times$ ULN
- ALT $\geq 5 \times$ ULN
- ALT $\geq 10 \times$ ULN
- ALT $\geq 20 \times$ ULN
- AST $\geq 3 \times$ ULN
- AST $\geq 5 \times$ ULN
- AST $\geq 10 \times$ ULN
- AST $\geq 20 \times$ ULN
- TBL $\geq 2 \times$ ULN
- Alkaline phosphatase $\geq 1.5 \times$ ULN
- ALT and/or AST $\geq 3 \times$ ULN and concurrent TBL $\geq 1.5 \times$ ULN
- ALT and/or AST $\geq 3 \times$ ULN and concurrent TBL $\geq 2 \times$ ULN

10.3.3 Analysis of Long Term Laboratory Data**10.3.3.1 Assessment of Mean Change from Baseline and Mean Percentage Change from Baseline in Clinical Laboratory Variables**

Analyses of mean change from baseline in continuous hematology, chemistry, and urinalysis variables which are measured longitudinally will be performed by visits and by "as treated" treatment group sequences as described in Section 10.1. For each change from baseline analysis, the following summary statistics will be presented for each treatment group: sample size, baseline mean, visit mean, and the mean, standard deviation, and median of the changes from baseline.

In addition, similar analyses will be conducted for mean percentage change from baseline in hemoglobin, NK cells, LDL, HDL and triglycerides.

10.3.3.2 Assessment of Potentially Clinical Significant Laboratory Values

Long term laboratory data will be summarized based on the number and percentage of subjects meeting the criteria for potentially clinical significant laboratory values and by the actual treatment received at the time of the event occurrence. The treatment groups are the same as the ones for long term AE analysis as described in Section 10.2.2. A subject can be counted under different treatment groups if he/she switched treatment and experienced potentially clinical significant laboratory values under different treatment groups.

A listing of all subjects with any laboratory determination meeting OMERACT criteria of Grade 3 or 4 will be provided by Grade. For creatine phosphokinase, creatinine, NCI CTC criteria will be used. For each of these subjects, the whole course of the respective parameter will be listed.

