10.2.3 Analysis of Long Term Adverse Event Rates

Long term adverse event rates will be analyzed using event rates adjusted by cumulative exposure and will be based on the actual treatment received at the time of AE occurrence. The detailed treatment groups are defined as follows.

1. Upadacitinib (ABT-494) 7.5 mg QD

This includes AEs occurred under Upadacitinib 7.5 mg QD exposure from subjects starting on Upadacitinib 7.5 mg QD and subjects switching from placebo to Upadacitinib 7.5 mg QD.

2. Upadacitinib (ABT-494) 15 mg QD

This includes AEs occurred under Upadacitinib 15 mg QD exposure from subjects starting on Upadacitinib 15 mg QD and subjects switching from placebo to Upadacitinib 15 mg QD.

3. Upadacitinib (ABT-494) 30 mg QD

This includes AEs occurred under Upadacitinib 30 mg QD exposure from subjects starting on Upadacitinib 30 mg QD and subjects switching from placebo to Upadacitinib 30 mg QD.

4. Placebo

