10.3.3.3 Assessment of Liver Elevations

The frequencies and percentages of subjects with post baseline liver specific function test values that meet the following criteria of potential clinical interest will be summarized by the actual treatment received at the time of the event occurrence similarly as described in Section 10.2.2:

- ALT $\geq 3 \times$ ULN
- ALT $\geq 5 \times$ ULN
- ALT $\geq 10 \times$ ULN
- ALT $\geq 20 \times$ ULN
- AST $\geq 3 \times$ ULN
- AST $\geq 5 \times$ ULN
- AST $\geq 10 \times$ ULN
- AST $\geq 20 \times$ ULN
- TBL $\geq 2 \times$ ULN
- Alkaline phosphatase $\geq 1.5 \times$ ULN
- ALT and/or AST $\geq 3 \times$ ULN and concurrent TBL $\geq 1.5 \times$ ULN
- ALT and/or AST $\geq 3 \times$ ULN and concurrent TBL $\geq 2 \times$ ULN

A subject can be counted under different treatment groups if he/she switched treatment and experienced potentially clinical significant laboratory values under different treatment groups.

A listing of potentially clinically significant liver elevations based on criteria specified above will be provided. For each of these subjects, the whole course of the respective parameter will be listed.

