10.4.3 Analysis of Long Term Vital Sign

Analyses of mean change from baseline in continuous vital signs variables which are measured longitudinally will be performed by visits and by "as treated" treatment group sequences as described in Section 10.1. For each change from baseline analysis, the following summary statistics will be presented for each treatment group: sample size, baseline mean, visit mean, and the mean, standard deviation, and median of the changes from baseline.

Long Term Vital Sign will also be summarized based on the number and percentage of subjects meeting the criteria for potentially clinical significant vital sign values and by the actual treatment received at the time of the event occurrence. The treatment groups are the same as the ones for long term AE analysis as described in Section 10.2.2. A subject can be counted under different treatment groups if he/she switched treatment and experienced potentially clinical significant laboratory values under different treatment groups.

A listing of all subjects with any vital sign values meeting the criteria for potentially clinically significant vital signs will be provided. For each of these subjects, the whole course of the respective parameter will be listed.

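### Long-term tables of abnormal laboratory, liver and vital-sign values show crude percentages for about 12 weeks of placebo beside years of upadacitinib, so those columns are not comparable

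*SAP*

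**What the plan says.** Three long-term safety tables are specified in the same way.

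- Laboratory (SAP 10.3.3.2): "Long term laboratory data will be summarized based on the number and percentage of subjects meeting the criteria for potentially clinical significant laboratory values", presented "by the actual treatment received at the time of the event occurrence".
- Liver (SAP 10.3.3.3): "The frequencies and percentages of subjects with post baseline liver specific function test values" that meet any of 12 criteria, which "will be summarized by the actual treatment received at the time of the event occurrence similarly" to the adverse event groups.
- Vital signs (SAP 10.4.3): "Long Term Vital Sign will also be summarized based on the number and percentage of subjects meeting the criteria", again by treatment at the event.

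Sections 10.3.3.2 and 10.4.3 take their groups from the long-term adverse event analysis. They cite Section 10.2.2, which covers Period 1; the long-term groups are defined in 10.2.3. These are the three upadacitinib doses, each pooling starters with subjects switched from placebo, and Placebo as a fourth group. Section 10.3.3.2 adds: "A subject can be counted under different treatment groups if he/she switched treatment". The only planned switch is from placebo to upadacitinib at Week 12, so a placebo column is intended.

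For the same groups, adverse events are handled differently: "Long term adverse event rates will be analyzed using event rates adjusted by cumulative exposure" (SAP 10.2.3). SAP 10.1 speaks of a rate of these laboratory and vital-sign values, but defines no denominator and then specifies frequency tables.

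**The concern.** A cumulative percentage grows with time on observation. Placebo time stops at Week 12. Upadacitinib time runs until approval in Japan; Protocol 5.6.4 expects about 3.5 years, and the exposure categories in SAP 8.0 extend to 4 years and beyond. The three sections give no person-time denominator, common time window or time-to-event method.

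A reader who compares adjacent columns will therefore see more subjects with abnormal values on upadacitinib even if the drug has no effect. The liver table carries the most risk of misreading, because its criteria include the combined aminotransferase and bilirubin elevations used to screen for potential Hy's law cases.

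**Working it through.** The plan states no event rate or expected percentage here, so there is no figure of its own to reproduce. The check asks what the tables would show if upadacitinib had no effect.

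**Inputs from the documents**
- Placebo: 3 × 16 = 48 subjects, 12 weeks = 84/365.25 = 0.230 years (SAP 4.2).
- Each upadacitinib dose: 48 starters + 16 switchers = 64 subjects (SAP 4.2).
- Follow-up T: about 3.5 years (Protocol 5.6.4); 1, 2 and 4 years also tried.

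**Assumptions**
- The same constant hazard λ of a first abnormality in every group, 1 to 10 per 100 patient-years.
- Discontinuation hazard d of 0 or 0.20 per year.
- The denominator is all subjects treated in that column.

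**Formula.** Percentage with an event by time t: R(t) = λ/(λ+d) × [1 − exp(−(λ+d)t)]. Placebo shows R(0.230). Each dose shows [48 × R(T) + 16 × R(T − 0.230)]/64.

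**Example** (λ = 0.05, d = 0, T = 3.5). Placebo: 1 − exp(−0.05 × 0.230) = 1.14%. Upadacitinib: 0.75 × 16.05% + 0.25 × 15.08% = 15.81%. Ratio 13.8.

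| λ per 100 patient-years | Placebo % | Upadacitinib % at 3.5 years, d = 0 | Ratio |
|---|---|---|---|
| 1 | 0.23 | 3.38 | 14.7 |
| 2 | 0.46 | 6.65 | 14.5 |
| 5 | 1.14 | 15.81 | 13.8 |
| 10 | 2.27 | 29.12 | 12.8 |

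**Other follow-up times**, ratio over the same range of λ:
- No discontinuation: 4.0 to 4.1 at 1 year, 7.8 to 8.4 at 2 years, 14.3 to 16.8 at 4 years.
- d = 0.20: 3.7 to 3.8 at 1 year, 6.6 to 7.1 at 2 years, 9.7 to 10.9 at 3.5 years.

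**Person-time** at 3.5 years without loss: 48 × 0.230 = 11.0 patient-years on placebo, against 48 × 3.5 + 16 × 3.27 = 220.3 per upadacitinib dose.

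**Would exposure-adjusted rates repair the placebo contrast?** Under the constant-hazard model, yes: first events per 100 patient-years at risk come out equal in all columns. But laboratory abnormalities are seen only when blood is drawn. Draws fall at Weeks 2, 4, 8 and 12 (SAP Table 5), then Weeks 16, 20, 24, 36, 48 and every 12 weeks. That gives 4 draws in 0.230 years on placebo (4/0.230 = 17.4 per year) and 20 in 3.5 years for starters (20/3.5 = 5.7 per year). If a transient abnormality had the same chance of being found at each draw (an assumption), the first-occurrence rate on placebo would be about 17.4/5.7 = 3 times that on upadacitinib. The bias would reverse.

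Under that per-draw model the crude percentages still favour placebo, but by less. Switchers have 16 draws after Week 12, so a dose group averages (48 × 20 + 16 × 16)/64 = 19 draws against 4, a ratio of up to 19/4 = 4.75 when the chance per draw is small.

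**The case against.** The strongest reply is that the valid comparison is already planned. SAP 10.3.2.3 (laboratory, with Fisher's exact tests), 10.3.2.4 (liver) and 10.4.2 (vital signs) compare combined placebo with each dose over the same 12 weeks. The long-term tables carry no test, difference or confidence interval, and exposure is tabulated for the same four groups in SAP 8.0. Where the SAP does contrast long-term safety with placebo (10.2.3.1, events of special interest), it uses exposure-adjusted rates. All of this stands, and it limits the point to how results are displayed. It does not justify a second placebo column that cannot be read against its neighbours.

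The adjusted adverse event rates do not replace these tables either, because Protocol 6.1.1.1 counts a laboratory abnormality as an adverse event only under set conditions.

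A reader might infer three stronger things that the documents do not support:

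- **That the dose comparison is also broken.** Each dose has the same 48 + 16 structure and visit schedule, so planned exposure is balanced. Only differential dropout could disturb it. That is possible, since Protocol 5.4.1 removes subjects who lack joint improvement from Week 24, but the documents give no figure for it.
- **That a 14-fold distortion is to be expected.** That needs full 3.5-year follow-up without loss. Period 2 has no fixed length, and the additional analyses for submission (SAP 4.4) could come earlier.
- **That using the adverse event method would settle it.** The rates in 10.2.3 count all events over total exposure, which is a different quantity from first occurrences over time at risk. The difference in sampling density also rules out a placebo contrast on either scale.

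**Conclusion.** The point holds as a misleading long-term display of placebo against upadacitinib in three tables. The trial keeps its fair placebo comparison, in Period 1.

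The direction follows from the design: with equal underlying risk, the longer-observed columns show higher percentages. The size depends on assumed rates, because the documents give none. With an equal constant hazard of 1 to 10 first events per 100 patient-years it is about 4-fold at 1 year, 8-fold at 2 years and 13- to 15-fold at 3.5 years without dropout, or 10- to 11-fold at 3.5 years with 20% annual discontinuation. If detection depends on the number of draws, it is at most about 4.75-fold at 3.5 years.

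**What to change.** 1. In SAP 10.3.3.2, 10.3.3.3 and 10.4.3, remove the placebo column from the long-term percentage tables and refer to 10.3.2.3, 10.3.2.4 and 10.4.2 for the comparison with placebo.
2. For the three upadacitinib doses, add the number of subjects with a first occurrence per 100 patient-years at risk, with time at risk ending at that first occurrence. This guards against differential dropout between doses. State that it differs from the all-events rates in 10.2.3 and is not to be compared with placebo.
3. Correct the cross-reference from Section 10.2.2 to Section 10.2.3 in all three places. SAP 10.1 has a similar slip, citing 10.2.2.2 for the long-term adverse event rates.

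Items 1 and 3 are wording only. Item 2 needs a small extra derivation: SAP 8.0 gives total exposure, so time to first occurrence must be derived for each laboratory parameter, each of the 12 liver criteria and each vital-sign criterion. No new data are needed.

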10.3.3.3 Assessment of Liver Elevations

The frequencies and percentages of subjects with post baseline liver specific function test values that meet the following criteria of potential clinical interest will be summarized by the actual treatment received at the time of the event occurrence similarly as described in Section 10.2.2:

- ALT $\geq 3 \times$ ULN
- ALT $\geq 5 \times$ ULN
- ALT $\geq 10 \times$ ULN
- ALT $\geq 20 \times$ ULN
- AST $\geq 3 \times$ ULN
- AST $\geq 5 \times$ ULN
- AST $\geq 10 \times$ ULN
- AST $\geq 20 \times$ ULN
- TBL $\geq 2 \times$ ULN
- Alkaline phosphatase $\geq 1.5 \times$ ULN
- ALT and/or AST $\geq 3 \times$ ULN and concurrent TBL $\geq 1.5 \times$ ULN
- ALT and/or AST $\geq 3 \times$ ULN and concurrent TBL $\geq 2 \times$ ULN

A subject can be counted under different treatment groups if he/she switched treatment and experienced potentially clinical significant laboratory values under different treatment groups.

A listing of potentially clinically significant liver elevations based on criteria specified above will be provided. For each of these subjects, the whole course of the respective parameter will be listed.

10.4 Analysis of Vital Signs

10.4.1 Variables and Criteria Defining Abnormality

Vital sign variables include sitting systolic blood pressure, sitting diastolic blood pressure, pulse rate, respiratory rate, body temperature, and weight. The criteria for potentially clinically significant vital sign findings are presented in [Table 15](#).

Table 15. Criteria for Potentially Clinically Significant Vital Sign Findings

Vital Sign	Category	Criteria for Potential Clinically Significant Vital Signs
Systolic blood pressure	Low	Value \leq 90 mmHg and decrease \geq 20 mmHg from Baseline
	High	Value \geq 160 mmHg and increase \geq 20 mmHg from Baseline
Diastolic blood pressure	Low	Value \leq 50 mmHg and decrease \geq 15 mmHg from Baseline
	High	Value \geq 105 mmHg and increase \geq 15 mmHg from Baseline
Pulse	Low	Value \leq 50 bpm and decrease \geq 15 bpm from Baseline
	High	Value \geq 120 bpm and increase \geq 15 bpm from Baseline
Respiratory Rate	Low	< 10 rpm
	High	> 24 rpm
Body temperature	High	> 39.0 degrees C (102.3 degrees F)
Weight	High	> 7% increase from baseline
	Low	> 7% decrease from baseline

10.4.2 Analysis of Vital Sign for Period 1

Analyses of mean change from baseline in continuous vital sign variables which are measured longitudinally will be performed by visits and by the "as treated" treatment groups of Upadacitinib 7.5 mg QD, Upadacitinib 15 mg QD, Upadacitinib 30 mg QD, and combined placebo groups. For each change from baseline analysis, the following summary statistics will be presented for each treatment group: sample size, baseline mean, visit mean, and the mean, standard deviation, and median of the changes from baseline. An ANOVA model with treatment as factor will be used to test statistical significance for the change from baseline mean among different treatment groups.

The number and percentage of subjects meeting the criteria for potentially clinically significant vital sign values will be summarized by "as treated" treatment group and overall.

10.4.3 Analysis of Long Term Vital Sign

Analyses of mean change from baseline in continuous vital signs variables which are measured longitudinally will be performed by visits and by "as treated" treatment group sequences as described in Section 10.1. For each change from baseline analysis, the following summary statistics will be presented for each treatment group: sample size, baseline mean, visit mean, and the mean, standard deviation, and median of the changes from baseline.

Long Term Vital Sign will also be summarized based on the number and percentage of subjects meeting the criteria for potentially clinical significant vital sign values and by the actual treatment received at the time of the event occurrence. The treatment groups are the same as the ones for long term AE analysis as described in Section 10.2.2. A subject can be counted under different treatment groups if he/she switched treatment and experienced potentially clinical significant laboratory values under different treatment groups.

A listing of all subjects with any vital sign values meeting the criteria for potentially clinically significant vital signs will be provided. For each of these subjects, the whole course of the respective parameter will be listed.

10.5 Analysis of ECG Parameters

10.5.1 Variables

ECG is collected at baseline visit, and Week 24/Prematurely discontinue. ECG findings will be summarized by treatment group for each parameter and visit.

11.0**Appendix****Appendix A****OMERACT Criteria**

Appendix A. OMERACT Criteria

Rheumatology Common Toxicity Criteria v.2.0

Based on Woodworth TG, et al. Standardizing assessment of adverse effects in rheumatology clinical trials II. Status of OMERACT Drug Safety Working Group May 2006: OMERACT 8. Standardizing Assessment and Reporting of Adverse Effects in Rheumatology Clinical Trials: Enabling Description of Comparative Safety Profiles for Antirheumatic Therapies

Rheumatology Common Toxicity Criteria v.2.0			
Based on Woodworth TG, et al. Standardizing assessment of adverse effects in rheumatology clinical trials II. Status of OMERACT Drug Safety Working Group May 2006: OMERACT 8. Standardizing Assessment and Reporting of Adverse Effects in Rheumatology Clinical Trials: Enabling Description of Comparative Safety Profiles for Antirheumatic Therapies			
4 – Includes Life Threatening			
1 – Mild	2 – Moderate	3 – Severe	4 – Includes Life Threatening
Asymptomatic, or transient Short duration (< 1 week) No change in life style No medication or OTC	Symptomatic Duration (1 – 2 weeks) Alter lifestyle occasionally Meds relieve. (may be prescription), Study drug continued	Prolonged symptoms, reversible, major or functional impairment Prescription meds/partial relief May be hospitalized < 24 hr Temporary study drug discontinuation, or/and dose reduced	At risk of death Substantial disability, especially if permanent. Multiple meds Hospitalised > 24 hr Study drug discontinued
A. Allergic/Immunologic			
A1. Allergic reaction/ hypersensitivity (includes drug fever)	Transient rash: drug fever < 38°C; transient, asymptomatic bronchospasm	Generalised urticaria responsive to meds; or drug fever > 38°C, or reversible bronchospasm	Symptomatic bronchospasm requiring meds; symptomatic urticaria persisting with meds, allergy related oedema/angioedema
A2. Autoimmune reaction	Serologic or other evidence of autoimmune reaction, but patient asymptomatic: all organ function normal and no treatment is required (e.g., vitiligo)	Evidence of autoimmune reaction involving a non-essential organ or functions, requiring treatment other than immunosuppressive drugs (e.g., hypothyroidism)	Reversible autoimmune reaction involving function of a major organ or toxicity requiring short term immunosuppressive treatment (e.g., transient colitis or anaemia)
A3. Rhinitis (includes sneezing, nasal stuffiness, post nasal discharge)	Transient, non-prescription meds relieve	Prescription med. required, slow med. with persistent disabling symptoms such as impaired exercise tolerance	NA

A. Allergic/Immunologic (Continued)

A4. Serum sickness	Transient, non-prescription meds relieve	Symptomatic, slow response to meds (e.g., oral corticosteroids)	Prolonged; symptoms only partially relieved by meds; parenteral corticosteroids required	Major organ dysfunction, requires long-term high-dose immunosuppressive therapy
A5. Vasculitis	Localised, not requiring treatment; or rapid response to meds; cutaneous	Symptomatic, slow response to meds (e.g., oral corticosteroids)	Generalised, parenteral corticosteroids required or/and short duration hospitalisation	Prolonged, hospitalisation, ischemic changes, amputation
B. Cardiac				
B1. Arrhythmia	Transient, asymptomatic	Transient, but symptomatic or recurrent, responds to meds	Recurrent/persistent; maintenance prescription	Unstable, hospitalisation required, parenteral meds
B2. Cardiac function decreased	Asymptomatic decline in resting ejection fraction by > 10%, but < 20% of baseline value	Asymptomatic decline of resting ejection fraction \geq 20% of baseline value	CHF responsive to treatment	Severe or refractory CHF
B3. Edema	Asymptomatic (e.g., 1+ feet/calves), self-limited, no therapy required	Symptomatic (e.g., 2+ feet/calves), requires therapy	Symptoms limiting function (e.g., 3+ feet/calves, 2+ thighs), partial relief with treatment prolonged	Anasarca; no response to treatment
B4. Hypertension (new onset or worsening)	Asymptomatic, transient increase by > 20 mmHg (diastolic) or to > 150/100 if previously normal, no therapy required	Recurrent or persistent increase > 150/100 or by > 10 mmHg (diastolic), requiring and responding readily to treatment	Symptomatic increase > 150/100, > 20 mmHg, persistent, requiring multi agency therapy, difficult to control	Hypertensive crisis
B5. Hypotension (without underlying diagnosis)	Transient, intermittent, asymptomatic, orthostatic decrease in blood pressure > 20 mmHg	Symptomatic, without interference with function, recurrent or persistent > 20 mmHg decrease, responds to treatment	Syncope or symptomatic, interferes with function, requiring therapy and sustained medical attention, dose adjustment or drug discontinuation	Shock
B6. Myocardial ischaemia	Transient chest pain/ECG changes; rapid relief with nitro	Recurring chest pain, transient ECG ST-T changes; treatment relieves	Angina with infarction, no or minimal functional compromise, reduce dose or discontinue drug	Acute myocardial infarction, arrhythmia or/and CHF

B. Cardiac (Continued)			
B7. Pericarditis/ pericardial effusion	Rub heard, asymptomatic	Detectable effusion by echocardiogram, symptomatic NSAID required	Detectable on chest x-ray, dyspnoea; or pericarditis; requires corticosteroids
B8. Phlebitis/thrombosis/ Embolism (excludes injection sites)	Asymptomatic, superficial, transient, local, or no treatment required	Symptomatic, recurrent, deep vein thrombosis, no anticoagulant therapy required	Deep vein thrombosis requiring anticoagulant therapy
C. General (Constitutional)			
C1. Fatigue/malaise (asthenia)	Increase over baseline; most usual daily functions maintained, short term	Limits daily function intermittently over time	Interferes with basic ADL, persistent
C2. Fever (pyrexia) (note: fever due to drug allergy should be coded as allergy)	Transient, few symptoms 37.7 – 38.5°C	Symptomatic, recurrent 38.6 – 39.9°C. Relieved by meds	≥ 40°C, ≤ 24 h, persistent symptoms; partial response to meds
C3. Headache	Transient or intermittent, no meds or relieved with OTC	Persistent, recurring, non-narcotic analgesics relieve	Prolonged with limited response to narcotic medicine
C4. Insomnia	Difficulty sleeping, short term, no interfering with function	Difficulty sleeping interfering with function, use of prescription med	Prolonged symptoms, with limited response to narcotic meds
C5. Rigors, chills	Asymptomatic, transient, no meds, or non-narcotic meds relieve	Symptomatic, narcotic meds relieve	Prolonged symptoms, with limited response to narcotic meds
C6. Sweating (diaphoresis)	Episodic, transient	Frequent, short term	Frequent, drenching, disabling
C7. Weight gain	5% – 9.9%	10% – 19.9%	20% – 30%
C8. Weight loss	5% – 9.9%	10% – 19.9%	20% – 30%

D. Dermatologic					
D1. Alopecia	Subjective, transient	Objective, fully reversible	Patchy, wig used, partly reversible	Complete, or irreversible even if patchy	
D2. Bullous eruption	Localised, asymptomatic	Localised, symptomatic, requiring treatment	Generalised, responsive to treatment; reversible	Prolonged, generalised, or requiring hospitalisation for treatment	
D3. Dry skin	Asymptomatic, controlled with emollients	Symptoms eventually (1 – 2 wks) controlled with emollients	Generalised, interfering with ADL > 2 wks, persistent pruritis, partially responsive to treatment	Disabling for extended period, unresponsive to ancillary therapy and requiring study drug discontinuation for relief	
D4. Injection site reaction	Local erythema, pain, pruritis, < few days	Erythema, pain, oedema, may include superficial phlebitis, 1 – 2 wks	Prolonged induration, superficial ulceration; includes thrombosis	Major ulceration necrosis requiring surgery	
D5. Petechiae (without vasculitis)	Few, transient asymptomatic	Dependent areas, persistent up to 2 wks	Generalised, responsive to treatment; reversible	Prolonged, irreversible, disabling	
D6. Photosensitivity	Transient erythema	Painful erythema and oedema requiring topical treatment	Blistering or desquamation, requires systematic corticosteroids	Generalised exfoliation or hospitalisation	
D7. Pruritis	Localised, asymptomatic, transient, local treatment	Intense, or generalised, relieved by systematic medication	Intense or generalised; poorly controlled despite treatment	Disabling, irreversible	
D8. Rash (not bullous)	Erythema, scattered macular/popular eruption	Diffuse macular/popular eruption or erythema with pruritis; dry desquamation; treatment required	Generalised, moist desquamation, requires systemic corticosteroids; responsive to treatment; reversible	Exfoliative or ulcerating, or requires hospitalisation; or parenteral corticosteroids	
D9. Induration/fibrosis/Thickening (not sclerodermal)	Transient; TOC or no meds	Localized, high density on palpation, reversible, no effect on ADL and not disfiguring	Local areas < 50% body surface, not disfiguring, transient interference with ADL, reversible	Disabling, irreversible, systemic symptoms	

E. Ear/Nose/Throat	
E1. Hearing loss	Transient, intermittent, no interference with function
E2. Sense of smell	Slightly altered
E3. Stomatitis	Asymptomatic
E4. Taste disturbance (dysgeusia)	Transiently altered; metallic
E5. Tinnitus	Intermittent, transient, no interference with function
E6. Voice changes (includes hoarseness, loss of voice, laryngitis)	Intermittent hoarseness, able to vocalise
E7. Xerostomia (dry mouth)	Transient dryness
F. Eye/Ophthalmologic	
F1. Cataract	Asymptomatic, no change in vision, non-progressive
F2. Conjunctivitis	Asymptomatic, transient, rapid response to treatment
F3. Lacrimation increased (tearing, watery eyes)	Symptoms not requiring treatment, transient

F. Eye/Ophthalmologic (Continued)

F4. Retinopathy	Asymptomatic, non-progressive, no treatment	Reversible change in vision; readily responsive to treatment	Disabling change in vision ophthalmological findings reversible, sight improves over time	Loss of sight
F5. Vision changes (e.g., blurred, photophobia, night blindness, vitreous floaters)	Asymptomatic, transient, no treatment required	Symptomatic, vision changes not interfering with function, reversible	Symptomatic, vision changes interfering with function	Loss of sight
F6. Xerophthalmia (dry eyes)	Mild scratchiness	Symptomatic without interfering with function, requires artificial tears	Interferes with vision/function, corneal ulceration	Loss of sight
G. Gastrointestinal				
G1. Anorexia	Adequate food intake, minimal weight loss	Symptoms requiring oral nutritional supplementation	Prolonged, requiring iv support	Requires hospitalization for nutritional support
G2. Constipation	Asymptomatic, transient, responds to stool softener, OTC laxatives	Symptomatic, requiring prescription laxatives, reversible	Obstipation requiring medical intervention	Bowel obstruction. Surgery required
G3. Diarrhea	Transient, increase of 2 – 3 stools/day over pre-treatment (no blood or mucus), OTC agents relieve	Symptomatic, increase 4 – 6 stools/day, nocturnal stools, cramping, requires treatment with prescription meds	Increase > 6 stools/day, associated with disabling symptoms, e.g., incontinence, severe cramping, partial response to treatment	Prolonged, dehydration, unresponsive to treatment, requires hospitalization
G4. Dyspepsia (heartburn)	Transient, intermittent, responds to OTC antacids, H-2 blockers	Prolonged, recurrent, requires prescription meds, relieved by prescription meds	Persistent despite treatment, interferes with function, associated with GI bleeding	NA
G5. GI bleed (gastritis, gastric or duodenal ulcer diagnosed-define aetiology)	Asymptomatic, endoscopic finding, haemocult + stools, no transfusion, responds rapidly to treatment	Symptomatic, transfusion ≤ 2 units needed; responds to treatment	Haematemesis, transfusion 3 – 4 units, prolonged interference with function	Recurrent, transfusion > 4 units, perforation, requiring surgery, hospitalisation

G. Gastrointestinal (Continued)

G6. Haematochezia (rectal bleeding)	Haemorrhoidal, asymptomatic, no transfusion	Symptomatic, transfusion ≤ 2 units, reversible	Recurrent, transfusion $> 3 - 4$ units	> 4 units, hypotension, requiring hospitalization
G7. Hepatitis	Laboratory abnormalities, asymptomatic, reversible	Symptomatic laboratory abnormalities, not interfering with function, slowly reversible	Laboratory abnormalities persistent > 2 wks, symptoms interfere with function	Progressive, hepato-renal, anasarca, pre-coma or coma
G8. Nausea, or nausea/vomiting (use diagnostic term)	Transient, intermittent, minimal interference with intake, rapid response to meds	Persistent, recurrent, requires prescription meds, intake maintained	Prolonged, interferes with daily function and nutritional intake, periodic iv fluids	Hypotensive, hospitalization, parenteral nutrition, unresponsive to out-patient management
G9. Pancreatitis	Anylast elevation, intermittent nausea/vomiting, transient, responds rapidly to treatment	Amylase elevation with abdominal pain, nausea, occasional vomiting, responsive to treatment	Severe, persistent abdominal pain with pancreatic enzyme elevation, incomplete or slow response to treatment	Complicated by shock, haemorrhage (acute circulatory failure)
G10. Proctitis	Perianal pruritus, haemorrhoids (new onset), transient, or intermittent, relieved by OTC meds	Tenesmus or ulcerations, anal fissure, responsive to treatment, minimal interference with function	Unresponsive to treatment, marked interference with function	Mucosal necrosis with haemorrhage, infection, surgery required
H. Musculoskeletal				
H1. Avascular necrosis	Asymptomatic MRI changes, non-progressive	MRI changes and symptoms responsive to rest and analgesia	MRI changes, symptoms requiring surgical intervention	Wheelchair bound; surgical repair not possible
H2. Arthralgia	Intermittent transient symptoms, no meds or relieved by OTC meds	Persistent or recurrent symptoms, resolve with meds, little effect on function	Severe symptoms despite meds impairs function	Debilitating, hospitalisation required for treatment
H3. Leg cramps	Transient, intermittent, does not interfere with function	Recurrent symptoms, minimally interferes with function or sleep, responds to meds	Persistent, prolonged interference with function or sleep, partial or no response to meds	NA
H4. Myalgia	Occasional; does not interfere with function	Frequent, requires meds (non-narcotic); minor effects on function	Major change in function/lifestyle, narcotic pain meds	Debilitating, profound weakness, requires wheelchair, unresponsive to meds

I. Neuropsychiatric			
11. Anxiety or Depression (mood alteration)	Symptomatic, does not interfere with function; no meds	Frequent symptoms, responds to meds; interferes with ADL at times	Persistent, prolonged symptoms, partial or no response to meds, limits daily function
12. Cerebrovascular ischaemia	NA	Single transient ischaemic event, responsive to treatment	Recurrent transient ischaemic events
13. Cognitive disturbance	Subjective symptoms, transient, intermittent, not interfering with function	Objective symptoms, persisting, interferes with daily function occasionally	Cerebrovascular vascular accident with permanent disability
14. Depressed consciousness (somnolence)	Observed, transient, intermittent, not interfering with function	Somnolence or sedation, interfering with function	Debilitating/disabling and permanent; toxic psychosis
15. Inability to concentrate	Subjective symptoms, does not interfere with function	Objective findings, interferes with function	Persistent, progressive, obtundation, stupor
16. Insomnia (in absence of pain)	Occasional difficulty sleeping, transient intermittent, not interfering with function	Recurrent difficulty sleeping; requires meds for relief; occasional interference with function	Persistent, prolonged objective findings or organic cause
17. Libido decreased	Decrease in interest	Loss of interest; influences relationship	Persistent or worsening difficulty sleeping; severely interferes with routine daily function
18. Peripheral motor neuropathy	Subjective or transient loss of deep tendon reflexes; function maintained	Objective weakness, persistent, no significant impairment of daily function	Persistent, prolonged interference with function
19. Peripheral sensory neuropathy (sensory disturbance)	Subjective symptoms without objective findings, transient, not interfering with function	Objective sensory loss, persistent, not interfering with function	Paralysis
110. Seizure	NA	Recurrence of old seizures, controlled with adjustment of medication	Recurrence not controlled, requiring hospitalization; new seizures

I. Neuropsychiatric (Continued)			
111. Vertigo (dizziness)	Subjective symptoms, transient, intermittent, no treatment	Objective findings, recurrent, meds relieve, occasionally interfering with function	Persistent, prolonged, interfering with daily function; partial response to medication
J. Pulmonary			
J1. Asthma	Occasional wheeze, no interference with activities	Wheezing, requires oral meds, occasional interference with function	Debilitating, requires nasal O ₂
J2. Cough	Transient, intermittent, occasional OTC meds relieve	Persistent, requires narcotic or other prescription meds for relief	Recurrent, persistent coughing spasms without consistent relief by meds, interferes with function
J3. Dyspnea	Subjective, transient, no interference with function	Symptomatic, intermittent or recurring, interferes with exertional activities	Symptomatic during daily routine activities, interferes with function, treatment with intermittent nasal O ₂ relieves
J4. Pleuritic pain (pleurisy)	Transient, intermittent symptoms, no treatment or OTC meds relieve	Persistent symptoms, requires prescription meds for relief	Prolonged symptoms, interferes with function, requires frequent narcotic pain relief
J5. Pneumonitis (pulmonary infiltrates)	Asymptomatic radiographic changes, transient, no treatment required	Symptomatic, persistent, requiring corticosteroids	Symptomatic, requiring treatment including O ₂
J6. Pulmonary function decreased (FVC or carbon monoxide diffusion capacity – DLCO)	76% – 90% of pre-treatment value	51% – 75% of pre-treatment value	26% – 50% of pre-treatment value $\leq 25\%$ of pre-treatment value

Laboratory Data			
K. Haematology			
K1. Hgb (g/dl) decrease from pre treatment	1.0 – 1.4	1.5 – 2.0	2.1 – 2.9, or Hgb < 8.0, > 7.0
K2. Leukopenia (total WBC) × 1000	3.0 – 3.9	2.0 – 2.9	1.0 – 1.9
K3. Neutropenia (× 1000)	1.5 – 1.9	1.0 – 1.4	0.5 – 0.9
K4. Lymphopenia (× 1000)	1.5 – 1.9	1.0 – 1.4	0.5 – 0.9
K5. Platelets (× 1000)	75 – LLN	50 – 74.9	20 – 49.9; platelet transfusion required
L. Chemistry			
L1. Hypercalcaemia (mg/dl)	1.1 × ULN – 11.5	11.6 – 12.5	12.6 – 13.5; or symptoms present
L2. Hyperglycemia (mg/dl) Fasting	140 – 160	161 – 250	251 – 500
L3. Hyperkalaemia (mmol/l)***	5.5 – 5.9	6.0 – 6.4	6.5 – 7.0 or any ECG change
L5. Hypocalcaemia (mg/dl)	0.9 × LLN – 7.8	7.7 – 7.0	6.9 – 6.5; or associated with symptoms
L6. Hypoglycemia (mg/dl)	55 – 64 (no symptoms)	40 – 54 (or symptoms present)	30 – 39 (symptoms impair function)
L7. Hyponatraemia (mmol/l)***	-	125 – 129	120 – 124
